4.7.1.2 Modifications of Study Therapy

Subjects with dosing modifications due to change in weight tier will be identified in a subject listing.

4.7.1.3 Corticosteroid Treatment

Subjects must be receiving CS (prednisone, prednisolone, or deflazacort) for at least 6 months prior to the start of study drug, with no significant change in dosage (> 0.2 mg/kg prednisone or > 0.24 mg/kg deflazacort) or dosing regimen for at least 3 months prior to the start of study drug, with the expectation that dosage and dosing regimen will not change significantly for the duration of the study.

For subjects where the dosing frequency is specified, calculated daily dose of CS at baseline will be summarized. Baseline is defined as the last regimen period before the first dose of study drug. Also, a listing of subjects with absolute change in CS ($[\text{calculated daily dose}]/[\text{body weight}]$) from baseline > 0.2 mg/kg prednisone or > 0.24 mg/kg deflazacort will be provided specifying their date and direction of change (increase or decrease). In case of a post-baseline change in CS drug, the following relationship will be used to calculate change from baseline:

1 mg prednisone = 1 mg prednisolone = 1.2 mg deflazacort

4.7.2 Adverse Events

AEs with onset on or after the first dose, and AEs with an onset date prior to first dose continuing into the treatment period and showing worsening (indicated by an overall severity higher than the initial severity) will be considered treatment-emergent for all analyses of the AE data. All AEs will be summarized by SOC and PTs for each treatment group.

The incidence of AEs will be characterized by the proportion of subjects having an AE, the number of subjects experiencing the event divided by the total number of subjects receiving study treatment. Regardless of the presence of SOC in a summary table, a decreasing order of incidence rates will be used for PTs in summary tables for AEs.

Where a subject has multiple AEs within the same system organ class in a single analysis period, the subject will only be counted once at the system organ class level in AE frequency tables.

Where a subject has the same AE, based on preferred terminology, reported multiple times in a single analysis period, the subject will only be counted once at the preferred terminology level in AE frequency tables.

Adverse event summary tables will be generated to summarize overall incidence, with additional tables summarizing results by intensity and by relationship to study medication. Serious adverse events will be summarized separately. Listings will be provided for serious AEs, AEs leading to discontinuation, and AEs without recorded resolution.

In addition, for subjects with events of hypersensitivity reactions and injection site reactions, summary tables (of overall incidence and by intensity) will be provided. MedDRA baskets based on Standardised MedDRA Queries, PT, high-level group terms, and high-level terms will be used as appropriate to identify the events to be included in these analyses. Additional baskets for summarizing AEs will be defined prior to the final analysis.

A by-subject listing of death will be provided for all reported deaths after a subject is enrolled (i.e., has signed the informed consent).

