### Study Treatment:

Each participant will be administered weekly, SC doses of RO7239361 (previously, BMS-986089) or placebo for 48 weeks in a randomized, double-blind design. Participants who complete the 48-week double-blind phase are eligible to receive OL RO7239361 (active treatment) as part of an OL extension phase of this study. The OL extension phase will last up to 192 weeks or until RO7239361 is commercially available in the subject's country, per local regulations, or the study is terminated by the Sponsor, whichever comes first. Please refer to [Section 7.8](#) for details regarding treatment after the end of study. Doses in the OL extension phase may be adjusted based on emerging data.

| Study Drug                 |                            |           |
|----------------------------|----------------------------|-----------|
| Medication                 | Potency                    | IP/Non-IP |
| RO7239361 7.5 mg dose      | 10.7 mg/mL (0.7mL/syringe) | IP        |
| RO7239361 15 mg dose       | 21.4 mg/mL (0.7mL/syringe) | IP        |
| RO7239361 35 mg dose       | 50 mg/mL (0.7mL/syringe)   | IP        |
| RO7239361 50 mg dose       | 71.4 mg/mL (0.7mL/syringe) | IP        |
| RO7239361 matching placebo | 0 mg/mL (0.7mL/syringe)    | IP        |

Other medications used as support medication for preventative, diagnostic, or therapeutic reasons, as components of the standard of care for a given diagnosis, may be considered as non-investigational products. In this study, corticosteroids are considered *a* non-investigational product and will not be provided by the sponsor.

Study drug preparation and administration instructions will be provided in a separate manual.

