randomized. Subjects originally randomized to placebo will be randomized to the high or low dose of RO7239361 on Day 1 of the open-label phase. Dose assignment in the open-label phase may be modified based upon emerging safety findings. Subjects entering the open-label phase will remain blinded to their original and current dose assignment. Any subject who discontinues the study early or who does not enter the open-label phase will enter the follow up phase of the study. The follow up phase of the study is up to 24 weeks. Subjects will be monitored for safety at three visits in the follow up phase. If RO7239361 anti-drug antibodies (ADAs) are present at the last on-treatment visit, the subject should provide immunogenicity samples at all follow up visits. Subjects who enter the follow up phase will undergo ADA monitoring during the follow up visits, which will occur at regular intervals for 24 weeks. The study design schematic is presented below.

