4.7 SAFETY ANALYSES

Adverse events, including abnormal laboratory findings, will be defined using the National Cancer Institute (NCI) Common Terminology for Adverse Events (CTCAE, version 5), and will be coded according to the most recent Medical Dictionary for Regulatory Activities (MedDRA) version. Adverse events will be summarized according to the MedDRA coded Preferred Terms (PT) by System Organ Class (SOC). Previous and concomitant medications will be coded using the WHO Drug Dictionary version.

The evaluation of safety is based on clinical AEs, vital signs, echocardiogram, ECG results, and clinical laboratory results reported during the study. Cardiac MRI measures

may also be included in the safety assessment. Safety analyses will be performed using the treated subjects. For AEs, all enrolled subjects will be listed.

Safety analysis data displays will be generated for the following:

- the double-blind treatment period, with baseline defined as the last visit prior to the start of the double-blind treatment period
- all active treatment during both the double-blind and open-label treatment periods (excluding data from the placebo subjects during the double-blind period); for this analysis, baseline will be defined as the last visit prior to the start of active treatment for each subject (i.e., the start of double-blind treatment period for those subjects randomized to active treatment from study start, or the start of the open-label treatment period for those subjects randomized to double-blind placebo and who are switching to active treatment at the start of the OLE).

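### The only AE incidence measure is a crude proportion, which is hard to interpret in the uncontrolled all-active display where time on drug varies up to 240 weeks

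*SAP*

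**What the plan says.** SAP 4.7.2 gives one definition of AE incidence and does not limit it to a period: "The incidence of AEs will be characterized by the proportion of subjects having an AE", that is, "the number of subjects experiencing the event divided by the total number of subjects receiving study treatment". Its counting rule reads "Where a subject has the same AE, based on preferred terminology, reported multiple times in a single analysis period"; such a subject is counted once, however long the period is.

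SAP 4.7 asks for safety displays over two periods. The first is "the double-blind treatment period, with baseline defined as the last visit prior to the start of the double-blind treatment period". The second is "all active treatment during both the double-blind and open-label treatment periods (excluding data from the placebo subjects during the double-blind period". In the second, baseline is reset to the start of active drug for boys who began on placebo.

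Exposure differs widely in the second display. The Protocol synopsis (Study Treatment) gives drug "or placebo for 48 weeks in a randomized, double-blind design", and then: "The OL extension phase will last up to 192 weeks", or less if the drug becomes commercially available or the sponsor ends the study. SAP 2 adds: "Subjects originally randomized to placebo will be randomized to the high or low dose of RO7239361 on Day 1 of the open-label phase". These boys therefore start active drug 48 weeks later than the others.

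SAP 2.4 schedules efficacy and safety analyses when the double-blind period ends and at Week 96, and a final data analysis at study end. SAP 4.7.1 summarizes duration of exposure on its own. Neither document specifies an AE rate per patient-year, a time-to-first-event summary or a fixed exposure window.

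**The concern.** One definition serves two displays that are built differently. Over a fixed 48 weeks with concurrent arms, a proportion of subjects is a clear measure of risk. In the all-active display a boy with 240 weeks on drug has five times as long to record a first event as a boy with 48 weeks, yet each adds one to the denominator. The percentage then mixes the risk of the event with the time available to observe it.

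At stake is what the long-term safety tables can tell a reader. A higher percentage at a later cut may mean that risk rises with longer treatment, or only that more time has passed. The exposure table shows that follow-up is longer, but does not allow that to be separated out event by event.

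**Working it through.** The documents state no AE rate, so there is no planned figure to reproduce. The check asks how far a crude proportion moves when risk per unit time is constant and the drug adds nothing.

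**Inputs from the documents**
- Double-blind period 48 weeks; open-label phase at most 192 weeks (Protocol synopsis, Study Treatment).
- Allocation 1:1:1 with 53 boys per arm (SAP 2 and 2.3), so 106 start on active drug and 53 on placebo.
- Maximum active exposure: 48 + 192 = 240 weeks for original-active boys and 192 weeks for switchers. At the Week 96 analysis: 96 and 48 weeks.
- Assumed treatment discontinuation over the double-blind period: 5% (SAP 2.3).

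**Assumptions**
- Constant hazard λ of 0.1 or 0.2 per year, no drug effect, all placebo boys switch, and no dropout in the main calculation.

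**Formulas**
- Risk by week w: P(w) = 1 − exp(−λ × w / 52.18).
- All-active proportion = [106 × P(original-active weeks) + 53 × P(switcher weeks)] / 159, a 2:1 mix. If switchers divide evenly between doses (the documents do not state the ratio), each dose column has the same mix.

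**λ = 0.2 per year**
- P(48) = 16.8%, P(96) = 30.8%, P(192) = 52.1%, P(240) = 60.1%.
- Week 96 analysis: (2 × 30.8% + 16.8%) / 3 = 26.1%.
- Study end, full follow-up: (2 × 60.1% + 52.1%) / 3 = 57.5% (from unrounded values).

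**λ = 0.1 per year**
- P(48) = 8.8%.
- Week 96 analysis: 14.1%.
- Study end, full follow-up: 34.8%.

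**Effect of dropout.** This version starts from assumed 48-week risks of 5%, 10% and 20%, with λ = −ln(1 − risk)/48 per week.
- No dropout: 8.2%, 16.0% and 30.7% at Week 96; 21.3%, 38.8% and 64.5% at study end.
- With 5% dropout per 48 weeks carried forward (μ = −ln(0.95)/48), P(w) = λ/(λ+μ) × [1 − exp(−(λ+μ)w)], and 53 × 0.95 = 50.35 boys switch. The proportions become 7.9%, 15.4% and 29.6% at Week 96; 19.0%, 34.8% and 58.6% at study end.
- Dropout at the assumed rate lowers the drift but does not remove it.

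**Shape of the hazard.** If every event fell early in active treatment, before any boy's follow-up ended, the proportion would not drift at all. Events that cluster early, as injection-site reactions may, therefore inflate less than shown.

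**After the change.** A constant hazard of 0.1 or 0.2 per year is 10 or 20 first events per 100 patient-years in every window of time on drug. A rate that differs between windows would then point to changing risk or changing patients, not to longer follow-up alone.

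**The case against.** The strongest reply is that the randomized safety comparison is untouched. The protocol's secondary safety endpoint is a tabulation of unique participants with events, active arms against placebo, and the double-blind display delivers it over equal planned exposure. SAP 1 says the plan focuses on those 48 weeks. The all-active display has no placebo column, and no test, estimand or decision rule rests on it. That stands.

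A reader might infer that the SAP sets long-term active percentages against the 48-week placebo rate. It does not: it keeps the displays apart and excludes double-blind placebo data from the second. A reader might also infer that an exposure-adjusted rate would make that comparison valid. It would not. Open-label boys are older, their disease is progressive and they have no concurrent control.

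The size is also open to challenge. The hazards are assumptions, 192 weeks is a cap, entry to the open-label phase is optional, and some boys will stop early. This stands too, so the study-end figures are an upper bound for the assumed hazards and the Week 96 figures are the more realistic ones.

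Finally, there are partial safeguards: the exposure summary, successive analyses at Week 48, Week 96 and study end, and AE listings. They help, but none ties the number of first events to the time at risk. SAP 4.5, the open-label section, covers efficacy only, so no other plan for open-label AE analysis is named.

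**Conclusion.** The point holds as a limit on interpretation in one uncontrolled descriptive display. The crude proportion is right for the double-blind display. In the all-active display it rises with follow-up alone, so it cannot show whether risk on drug is stable, rising or falling.

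With assumed hazards of 0.1 to 0.2 per year, the drift is from 8.8%–16.8% at 48 weeks to 14.1%–26.1% at the Week 96 analysis, about 1.6 times. The values of 34.8%–57.5% at study end require every boy to complete the full open-label phase. All of these rest on a constant hazard, no drug effect and no dropout.

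The documents do not support calling this an invalid test or a flaw in the comparison with placebo. It is a cheap improvement worth making before the Week 96 analysis.

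**What to change.** In SAP 4.7.2, keep crude proportions for the double-blind display. For the all-active display, add:

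- patient-years at risk for each column;
- first events per 100 patient-years with 95% confidence intervals, for AEs, SAEs, injection-site reactions and hypersensitivity reactions;
- the same rates split by time on active drug: 0–48, 48–96 and over 96 weeks, counted from each boy's first active dose;
- a statement that these rates are descriptive and are not a controlled comparison with double-blind placebo.

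The cost is a few extra tables built from dosing and AE onset dates that the planned analyses already need. There are no new data or visits, and the primary analysis does not change. The drawback is that a rate assumes a roughly constant hazard within each window. The split eases this but does not remove it, and the last window will be sparse if the open-label phase ends early.

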4.7.3 Laboratory Data

Scheduled laboratory measurements and corresponding change from baseline values will be summarized by treatment and nominal visit for each laboratory test, in SI units.

The results of all protocol-specified clinical laboratory tests, as well as the normal range of laboratory results, will be listed in SI units.

The incidence of marked laboratory abnormalities (based on Roche Standard Reference and Marked Reference Ranges) will be summarized using descriptive statistics, for all parameters for which the Marked Reference Ranges are defined.

For all parameters for which NCI CTCAE grades are defined, summary tables showing the number of subjects with abnormal laboratory results (falling outside of the laboratory range of normal) based on the grading criteria will be provided.

Plots of mean lab test results over time over-plotted on a scatterplot of all subject results at each visit will be provided for alanine aminotransferase (ALT), aspartate aminotransferase (AST), total bilirubin, glutamate dehydrogenase assay, gamma-glutamyl transferase, and creatine kinase (CK).

Scatter plots of post-baseline maximum values will be provided for ALT vs. Total bilirubin and AST vs. Total bilirubin separately.

Double Y-axis trace plots over time will be provided for ALT and CK in the same graph.

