## 4 OBJECTIVES AND ENDPOINTS

**Table 4-1: Objectives and Endpoints**

| Objectives  | Endpoints  |
|---|--|
| 
Primary
 
 
• To compare the efficacy of RO7239361 to placebo in ambulatory boys with Duchenne muscular dystrophy
 
   | 
 
• The change from baseline in the North Star Ambulatory Assessment (NSAA) total score at Week 48 in RO7239361-treated participants compared to placebo-treated participants
 
   |
| 
Secondary
 
 
• To compare the efficacy of RO7239361 to placebo using the following tests:               
 
– 4 Stair Climb Velocity
 
– Stand from supine velocity
 
– 10 M walk/run velocity
 
– PODCI transfers and basic mobility subscale
 
– Proximal lower extremity flexor (knee extension and knee flexion) strength, measured using manual myometry
 
– 6 Minute Walk Distance (6MWD)
 
– Clinical Global Impression of Change (CGI-C)
 
– Stride velocity, as recorded by the ActiMyo device
 
 
 
• To assess the safety and tolerability of RO7239361 in boys with DMD as reflected by new or worsening lab abnormalities (as defined by CTCAE criteria), serious adverse events (SAEs) and adverse events (AEs) leading to discontinuation
 
 | 
 
• Change from baseline at Week 48 in RO7239361-treated participants compared to placebo-treated participants in:               
 
– 4 Stair Climb Velocity
 
– Stand from supine velocity
 
– 10 M walk/run velocity
 
– PODCI transfers and basic mobility subscale
 
– Proximal lower extremity flexor (knee extension and knee flexion) strength, measured using manual myometry
 
– 6 Minute Walk Distance (6MWD)
 
– Clinical Global Impression of Change (CGI-C)
 
– 95th percentile stride velocity, as recorded with the ActiMyo device in a subset of the overall study population
 
 
 
• Tabulations of the numbers of unique participants with new or worsening laboratory abnormalities, SAEs and AEs leading to discontinuation, in RO7239361 arms compared to the placebo arm
 
 |

|   |   |
|---|---|

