### 10.3.2 Safety Analyses

All safety analyses will be performed using treated subjects.

| Endpoint    | Statistical Analysis Methods   |
|-------------|--|
| Primary     | Not applicable   |
| Secondary   | Tabular summaries of SAEs, AEs leading to discontinuation and Grade 3 to 4 laboratory abnormalities will present the number and percentage of unique subjects with treatment emergent events. Adverse event summaries will be presented by system organ class (SOC) and preferred term (PT). All SAEs since enrollment will be listed. Grade 3 to 4 laboratory abnormalities will be summarized as proportions by baseline toxicity grade. |
| Endpoint    | Statistical Analysis Methods   |
| Exploratory | Will be described in the Statistical Analysis Plan finalized before database lock  |

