2.2.4 Safety Endpoints

- Incidence of treatment-emergent adverse events (AEs)
- Change from baseline in vital signs, electrocardiogram (ECG), and echocardiogram measures
- Change from baseline in safety laboratory measures
- Incidence of marked laboratory abnormalities, based on Roche Standard Reference and Marked Reference Ranges.

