3.2 DATA MONITORING

There will be an independent data monitoring committee (iDMC) for this study. The iDMC charter will document the iDMC scope, frequency of review, and membership.

The iDMC shall have access to partially unblinded data (coded treatment assignments) including but not limited to the following: the frequency and spectrum of serious adverse events (SAEs); Grades 3 to 4 laboratory abnormalities; occurrence of malignancies, if any; and other select AEs of interest. The iDMC shall act as an advisor to the Sponsor and have responsibility for safeguarding the subjects' interests, and will make recommendations to the Sponsor on the conduct of the study.

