10.3.2 Safety Analyses

All safety analyses will be performed using treated subjects.

Endpoint	Statistical Analysis Methods
Primary	Not applicable
Secondary	Tabular summaries of SAEs, AEs leading to discontinuation and Grade 3 to 4 laboratory abnormalities will present the number and percentage of unique subjects with treatment emergent events. Adverse event summaries will be presented by system organ class (SOC) and preferred term (PT). All SAEs since enrollment will be listed. Grade 3 to 4 laboratory abnormalities will be summarized as proportions by baseline toxicity grade.
Endpoint	Statistical Analysis Methods
Exploratory	Will be described in the Statistical Analysis Plan finalized before database lock

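### The SAP body omits the protocol's secondary safety endpoint of new or worsening CTCAE laboratory abnormalities, and its by-grade laboratory count states no comparison with baseline grade

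*SAP*

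**What the plan says.** **Protocol.** The secondary safety endpoint in Table 4-1, repeated in the Synopsis, is "Tabulations of the numbers of unique participants with new or worsening laboratory abnormalities, SAEs and AEs leading to discontinuation", active arms compared with placebo. The matching objective ties the grading to CTCAE: "new or worsening lab abnormalities (as defined by CTCAE criteria". No grade threshold is given. The secondary row of Section 10.3.2 is narrower. It calls for counts and percentages of unique subjects with treatment-emergent events, and adds that "Grade 3 to 4 laboratory abnormalities will be summarized as proportions by baseline toxicity grade".

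**SAP body.** Section 2.2.4 has two laboratory items. One is change from baseline in the measured values. The other is "Incidence of marked laboratory abnormalities, based on Roche Standard Reference and Marked Reference Ranges". Section 4.7.3 then plans two count tables: the marked abnormalities, and, for every parameter with CTCAE grades, "summary tables showing the number of subjects with abnormal laboratory results (falling outside of the laboratory range of normal) based on the grading criteria". Elsewhere the SAP body names Grade 3 to 4 laboratory abnormalities only among the data for the monitoring committee in Section 3.2: "Grades 3 to 4 laboratory abnormalities; occurrence of malignancies, if any".

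**SAP Appendix 1.** This reprints the protocol, so the SAP file does contain both the endpoint and the Section 10.3.2 text, beginning "Tabular summaries of SAEs, AEs leading to discontinuation and Grade 3 to 4 laboratory abnormalities will present the number and percentage of unique subjects".

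**The concern.** New or worsening is a statement about change from entry. A count of boys outside the normal range, even split by grade, is a statement about status. The two agree when everyone enters normal and differ when they do not.

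This protocol expects boys to enter abnormal. Its diagnosis criterion (6.1, item 2b) cites a raised creatine kinase. Its laboratory exclusion (6.2, item 3a) applies only to deviations beyond those expected in the target population. Its liver criteria (9.2.7) refer to multiples of baseline ALT as well as of the upper limit of normal.

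ALT also matters for safety. Section 3.3 reports aminotransferase elevations in rats dosed for 6 months. It considers them likely specific to rats, but commits to monitoring aminotransferases and bilirubin. For such a test, a status count records the disease at entry together with any effect of treatment.

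**Working it through.** The check is mainly a comparison of texts; the plan states no figure to reproduce.

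**1. Side by side**

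| Source | What is counted | CTCAE | Related to baseline grade |
|---|---|---|---|
| Protocol Table 4-1 | Unique participants, new or worsening, no grade threshold | Yes | Yes, by definition |
| Protocol 10.3.2 | Unique subjects, treatment-emergent Grade 3 to 4 | Yes | Yes, explicitly |
| SAP 2.2.4, 4.7.3 (marked) | Incidence against sponsor ranges | No | Not stated |
| SAP 4.7.3 (graded) | Subjects outside normal range, by grade | Yes | Not stated |

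Neither SAP count table meets either protocol row. The omission is not simply a matter of style. SAP 4.7 defines baseline for safety displays, 4.7.2 gives a worsening rule for adverse events, 4.7.5 plans categorical change from baseline for ECGs, and 4.7.7 uses a 4-fold titer rise from baseline for antibodies. The laboratory count tables have no such rule.

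**2. Does the protocol foresee a high entry ALT?** Let baseline ALT be B x ULN. Under Protocol 9.2.7, with no corresponding CPK rise, the ALT criteria are met above 5 x baseline, or above both 10 x ULN and 2 x baseline:

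threshold = min(5B, max(10, 2B)) x ULN

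| B | Threshold (x ULN) | Multiple of baseline |
|---|---|---|
| 1 | 5 | 5.0 |
| 2 | 10 | 5.0 |
| 3 | 10 | 3.3 |
| 4 | 10 | 2.5 |
| 5 | 10 | 2.0 |
| 6 | 12 | 2.0 |
| 10 | 20 | 2.0 |

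The 2 x baseline term matters only if 2B > 10, that is B > 5. The rule therefore provides for boys who enter above 5 x ULN. It also follows that an ALT rise short of a doubling, or one with a matching CPK rise, does not meet the ALT criteria. The bilirubin and symptom criteria in the same section are separate and need no ALT rise.

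**3. How entry abnormality acts on a status count.** Take the simplest row, any abnormality, with the planned 53 boys per arm. Assume a share p enters abnormal and stays so, equal across arms in expectation because of randomization. Let r1 and r0 be the rates of new abnormality among the other boys on active drug and placebo. Each arm shows p + (1-p)r, so the difference is (1-p)(r1 - r0).

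| Assumed p | Counted from entry, 53p | Largest possible excess, 53(1-p) |
|---|---|---|
| 25% | 13.25 | 39.75 |
| 50% | 26.5 | 26.5 |
| 75% | 39.75 | 13.25 |
| 100% | 53 | 0 |

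The sign is kept and the size shrinks: dilution, not systematic bias. Worsening among boys already abnormal does not appear in this row. These values of p are assumptions, and the row is simpler than the planned table. SAP 4.7.3 tabulates by grade, so a boy who moves from Grade 1 to Grade 3 would appear at Grade 3. The by-grade rows recover part of the loss.

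**4. Grade 3 to 4 rows.** If no boy enters at Grade 3 to 4, every later case at that level is new and nothing is lost. Each boy who enters there and stays adds one case that is not treatment-emergent.

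**The case against.** The strongest reply is that the analysis is already specified. In the Protocol 10.3.2 table only the exploratory row is deferred to the SAP, nothing in the SAP withdraws the secondary row, and SAP 2.1 points to the synopsis in Appendix 1. This stands for Grade 3 to 4. It does not supply the any-grade count of Table 4-1, and it leaves one file with two specifications for the laboratory tables.

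Second, SAP 4.7.3 may be under-specified rather than wrong: it does not say whether counts are per visit or worst post-baseline. That is fair, but no reading of the stated text brings in baseline grade.

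Third, there is real partial cover:

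- Laboratory findings can enter as adverse events ("Adverse events, including abnormal laboratory findings, will be defined using the National Cancer Institute (NCI) Common Terminology for Adverse Events (CTCAE, version 5") and pass through the treatment-emergent rule in SAP 4.7.2. Protocol 9.2.6 limits these to results that are clinically significant or serious, or that led to interruption, discontinuation or corrective therapy.
- Potential drug-induced liver injury is reported as serious, on ALT, bilirubin or symptom criteria.
- SAP 4.7.3 plans change-from-baseline summaries by visit, listings, and plots of ALT, AST, bilirubin, GLDH, GGT and creatine kinase.
- Creatine kinase change at Week 48 is an exploratory endpoint (SAP 2.2.3), analysed by mixed model (4.4.3).

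These make it unlikely that a large liver or muscle signal would go unseen. None counts subjects whose grade worsened.

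A reader might infer that the SAP ignores baseline for laboratory data, that the arm comparison is biased, or that the shares in the illustration estimate the loss. The documents support none of these. Change from baseline is planned, randomization balances entry status in expectation, and no baseline grades are given.

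**Conclusion.** The gap is real and should be closed. The SAP body does not carry a protocol secondary safety endpoint, and the count it plans in its place is not tied to baseline grade. The consequence is a descriptive table that can dilute a difference from placebo on tests where boys enter abnormal.

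The size cannot be computed. It depends on the baseline grade mix for each test, and could be nil for Grade 3 to 4 if no boy enters at that level. The relevance to creatine kinase and ALT rests on the protocol's own diagnosis, exclusion and liver criteria. Whether the sponsor's marked ranges include a baseline condition cannot be checked, because their content is not in the documents; in any case they are not CTCAE grades. No hypothesis test and no efficacy result is affected.

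**What to change.** - **SAP 2.2.4:** add the protocol's endpoint of unique participants per arm with new or worsening CTCAE laboratory abnormalities.
- **SAP 4.7.3:** for each graded parameter, count unique subjects per arm whose worst post-baseline grade exceeds their baseline grade, with baseline as already defined in SAP 4.7. Add a table of baseline grade by worst post-baseline grade per arm, which also delivers the Grade 3 to 4 summary of Protocol 10.3.2.
- **Scope:** reconcile Table 4-1 (any grade) with Section 10.3.2 (Grade 3 to 4), or state that the second is a subset of the first.
- **Housekeeping:** name one CTCAE version for the grading. Protocol 9.2.6 uses 4.0 for laboratory events and SAP 4.7 uses version 5; no effect of the difference is shown.

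The cost is a few extra descriptive tables from data already collected, specified before database lock.
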